4.0 TREATMENT PLAN**4.1 Treatment Dosage and Administration**

- 4.1.1 30mL of 0.25% bupivacaine will be administered to bilateral TAP using ultrasound or laparoscopic guidance in prostatectomies. 40ml 0.25%

bupivacaine unilateral will be administered in nephrectomy patients (weight based dosage permitting). Placebo groups will receive direct injection of bupivacaine into surgical wounds.

4.1.2 The anesthesia protocol will be at the discretion of the anesthesiologist, including premedication, induction of anesthesia, endotracheal intubation, and maintenance of sedation and neuromuscular blockade. Similarly, all patients will undergo standardized procedure for obtaining pneumoperitoneum and insertion of laparoscopic ports.

Patients in the UTAP group will receive abdominal wall nerve block by the anesthesia team with 30 cc of 0.25% Bupivacaine in bilateral TAP regions under ultrasound guidance (percutaneously) after obtaining general anesthesia. (unilateral 40ml for nephrectomies) Conversely, patients in the LTAP group will undergo bilateral nerve blocks by the surgical team under direct vision from an intraabdominal access after creating pneumoperitoneum and inserting the laparoscope. Patients in the Placebo will receive injection of bupivacaine directly into the surgical wound.

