The following is an overview of the randomization generation and management process. The trial coordinator will create an administrator account with sealedenvelope.com. Only the email address given when setting up the trial will be registered as the administrator email address and it can be used to change the password, delete the trial, or receive a list of all randomizations performed at any time. The study statistician will generate the randomization list in Sealedenvelope.com. Once the account for the trial has been opened and the randomization list generated; any designated user (designated by the account administrator) with the single password for the trial can carry out new randomizations. Online randomization is achieved by the user completing a form with the trial ID and password after providing a patient ID as well as surgical type for stratification purposes. An email notification is then generated displaying the next sequential treatment group assignment from the randomization list and sent to the email address given by the user randomizing and the administrator. Data and randomizations held by the sealed envelope randomization system cannot be

changed or edited by users. Sealed Envelope will not edit or delete any data held by the system.

Participants will be blinded from the type of block given. Investigators cannot be blinded due to the nature of the intervention; however allocation concealment will be implemented by use of the sealed envelope service described above.

Blinding:

Participants will be blinded to group allocation throughout the study. Due to the nature of the intervention, it is not possible to blind the investigator to group allocation.

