10.2 Sample Size and Accrual

For two-arm non-inferiority trials, issues such as choice of non-inferiority margin, constancy assumption, and assay sensitivity have been debated for years, and the statistical methodology has been challenged. Three-arm trials including the experimental treatment, an active reference treatment and a placebo are recommended in the guidelines of the ICH⁵ and EMEA/CPMP⁶ as a useful approach to the assessment of assay sensitivity providing the trial with internal validation. The placebo group affords an opportunity to test for non-inferiority directly without use of a fixed pre-specified non-inferiority margin thereby making the constancy assumption an irrelevant point and allows for direct testing of assay sensitivity by comparing the active reference to the placebo.

The objectives of this trial are two-fold: 1. to verify assay sensitivity by demonstrating that UTAP (the active reference) is superior to placebo at controlling 24 hour postoperative pain and 2. to demonstrate non-inferiority of LTAP (the experimental approach) to UTAP (the active reference) with respect to 24 hour postoperative pain control.

A step-down hierarchical hypothesis testing approach will be used to test the two hypotheses (co-primary endpoints). In the first step, to establish assay sensitivity, the alternative hypothesis that UTAP is superior to placebo will be tested:

$$H_{01}: \mu_{UTAP} \geq \mu_{Placebo}$$

$$H_{A1}: \mu_{UTAP} < \mu_{Placebo}$$

If and only if we reject the null hypothesis, H_{01} , thereby establishing assay sensitivity will we proceed to the second step, to demonstrate non-inferiority of LTAP to UTAP.

In the second step, to establish non-inferiority, the alternative hypothesis that LTAP is non-inferior to UTAP will be tested using the 'fractional approach'

introduced by Pigeot I et al (2003) where the effect estimate is based on the ratio of the differences in means between LTAP and placebo and UTAP and placebo⁷ :

$$H_{02}: \frac{\mu_{LTAP} - \mu_{Placebo}}{\mu_{UTAP} - \mu_{Placebo}} \leq \theta$$

$$H_{A2}: \frac{\mu_{LTAP} - \mu_{Placebo}}{\mu_{UTAP} - \mu_{Placebo}} > \theta$$

θ is a pre-specified fixed fraction of active reference effect (retention of effect). Koch and Tangen⁸ provide reasonable regions of θ for non-inferiority testing between 0.5 and 0.99.

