historical placebo-controlled trials with parameters listed in the table below and discussed in the introduction, the estimated pooled mean pain scores and (total variance) was 3.4 (1.50) in the placebo and 1.49 (1.77) in the UTAP groups. The random effects meta-analysis was conducted with the Comprehensive Meta-Analysis Software Version 3.3.070 (2013).¹²

Study name	Treatment	Mean	SD	Variance	Sample size
Hosgood (2012)	Placebo	3.70	2.00	4.00	22
Aniskevich (2014)	Placebo	4.00	2.30	5.29	11
Qu (2016)	Placebo	2.80	1.20	1.44	40
Fabrizio (2018)	Placebo	3.57	0.64	0.41	50
Random	Placebo	3.40		1.50	
Hosgood (2012)	UTAP	1.90	1.50	2.25	24
Aniskevich (2014)	UTAP	1.50	1.20	1.44	10
Qu (2016)	UTAP	0.84	0.59	0.35	40
Fabrizio (2018)	UTAP	1.80	0.82	0.67	50
Random	UTAP	1.49		1.77	

In accordance with ICH guidelines on statistical principles for clinical trials a type I error rate of 0.025 was used for this sample size calculation. Optimal sample size allocation was determined to follow a 2:2:1 ratio of LTAP:UTAP:Placebo. A total sample size of 235 is required with a 2:2:1 allocation ratio (94 LTAP, 94 UTAP and 47 Placebo) to achieve 90% power to establish non-inferiority of LTAP to UTAP with a fixed fraction of 0.50 (LTAP has to achieve more than 50% of the effect of UTAP compared to placebo to claim as non-inferior) assuming means and variances of 1.49 (1.77), 1.49 (1.77) and 3.40 (1.50) in the LTAP, UTAP and Placebo groups, respectively. This sample size calculation was performed using the PowerRet function of the 'ThreeArmedTrials' package with the following parameters:

```
power_RET(experiment = c(1.49,1.77), reference = c(1.49,1.77), placebo = c(3.4,1.5),Delta = 0.7, sig_level = 0.025, power= 0.9, allocation = c(2,2,1)/5,distribution = "normal")
```

The statistical evaluation will be performed in the first step by a two sample t-test for demonstrating superiority of UTAP over placebo. Group sample sizes of 94 and 47 for UTAP and placebo groups achieve over 99% power to reject the null hypothesis of equal or worse means when the population VAS pain score means (SDs) in the UTAP and Placebo groups are 1.50 (1.33) and 3.4 (1.22), respectively, with a significance level of 0.025 using a one-sided two-sample unequal-variance t-test. The calculation was performed with PASS Version 15.

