10.3 Data Analyses Plans

Analysis of Co-Primary Endpoints:

The distribution of VAS pain scores in each group will be examined and assessed for normality and homoscedasticity, visually, by generating probability-probability (P-P) plots, boxplots, stem-and-leaf plots and quantile-quantile (Q-Q) plots, and with the Shapiro-Wilk normality test. If necessary, a transformation of the data will be made to render appropriate for parametric testing. All analyses will be performed on patients who undergo surgery and have a 24 hour VAS pain score assessment. Balance on baseline characteristics (including gender, age at surgery, height, weight, BMI, and operative time) among the randomized groups will be assessed separately for each intervention, using the standardized difference. Any variable with an absolute standardized difference >0.52 (i.e., $1.96 \times 1/n_1 + 1/n_2$) for either intervention will be adjusted for in secondary analyses.^{13,14}

A step-down hierarchical hypothesis testing approach will be used to test the two hypotheses (co-primary endpoints). In the first step, to establish assay sensitivity, the alternative hypothesis that the 24-hour post-operative mean VAS pain score in the UTAP group is superior to that in the placebo group will be tested by a one-sided two sample t-test at the 0.025 level of significance ($H_{01}: \mu_{UTAP} \geq \mu_{Placebo}$ vs. $H_{A1}: \mu_{UTAP} < \mu_{Placebo}$).

If assay sensitivity is demonstrated in the first step by rejecting the null hypothesis, H_{01} , we will proceed to the second step of testing for non-inferiority of LTAP to UTAP. To establish non-inferiority, the alternative hypothesis that LTAP is non-inferior to UTAP will be tested using the ‘fractional approach’ introduced by Pigeot et al (2003) where the effect estimate is based on the ratio of the differences in means between LTAP and placebo and UTAP and placebo ($H_{02}: \frac{\mu_{LTAP} - \mu_{Placebo}}{\mu_{UTAP} - \mu_{Placebo}} \leq \theta$: vs. $H_{A2}: \frac{\mu_{LTAP} - \mu_{Placebo}}{\mu_{UTAP} - \mu_{Placebo}} > \theta$).

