θ is pre-specified as the fixed fraction of active reference effect (retention of effect) of 0.50 (LTAP has to achieve more than 50% of the effect of UTAP compared to placebo to claim as non-inferior). The second step will be carried out based on the Fieller’s one-sided 97.5% lower confidence bound for the ratio of $\mu_{LTAP} - \mu_{Placebo}$ and $\mu_{UTAP} - \mu_{Placebo}$. If the lower bound of the confidence interval is greater than 50% then the null hypothesis, H_{02} is rejected (LTAP (the experimental approach) retains more than 50% efficacy of UTAP (the active reference) then non-inferiority of LTAP to UTAP will be declared. The formula for calculating Fieller’s confidence bound is presented in Pigeot et al (2003) and will be implemented using The R package ‘ThreeArmedTrials’ developed by Tobias Muetze (2016).

Analysis of Secondary Endpoints:

The secondary endpoints of 24-hour cumulative post-operative opioid analgesic requirement expressed in morphine equivalent dose (MED), intraoperative time taken to complete the surgical block, total operating room time and surgical time will be summarized using median, 1st and 3rd quartiles and minimum and

maximum values. A Kruskal-Wallis analysis of variance will be used to compare the cumulative MED requirement (time to complete the surgical block, total operating room time and surgical time) among the three intervention groups with all pairwise comparisons made between groups using the Dwass-Steel-Critchlow-Fligner procedure (Dwass 1960; Steel 1960; Critchlow and Fligner 1991).¹⁵⁻¹⁷

The secondary endpoint of antiemetic medication use will be reported as the number and percentage of patients that require antiemetic medication during their hospital stay within each intervention group. A Chi-Square will be used to compare percentages across groups. A log-binomial regression model will be used to estimate and compare the prevalence ratios (PR) and corresponding 95% confidence intervals (CI) for antiemetic medication use among patients in the three intervention groups.

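### The 235-patient sample size belongs to a retention fraction of 0.70, but the stated power and the decision rule use 0.50

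*Combined protocol and SAP*

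**What the plan says.** The non-inferiority test asks whether LTAP retains more than a fraction theta of UTAP's effect over placebo on the 24-hour VAS score. Theta appears in four places.

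- Section 10.2, range: it cites a source for reasonable values of theta "for non-inferiority testing between 0.5 and 0.99".
- Section 10.2, sample size sentence: 235 patients at 2:2:1 are required "to achieve 90% power to establish non-inferiority of LTAP to UTAP with a fixed fraction of 0.50".
- Section 10.2, the `power_RET` call given as the source of that calculation: "Delta = 0.7, sig_level = 0.025, power= 0.9". Its means, variances, alpha, power and allocation match the sentence above it. Only the fraction differs.
- Section 10.3, analysis: theta is "pre-specified as the fixed fraction of active reference effect (retention of effect) of 0.50", and the rule follows: "If the lower bound of the confidence interval is greater than 50% then the null hypothesis" is rejected.

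The value 0.7 occurs nowhere else as a retention fraction. No section justifies either value or explains the difference.

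**The concern.** Theta is this trial's non-inferiority margin. If 235 came from 0.70, the claim of 90% power at 0.50 is false, and the sample size and the decision rule rest on different margins. A Fieller lower bound between 0.50 and 0.70 would pass the written rule and fail the criterion used for sizing. A reader of the results could not tell which loss of effect the trial was designed to rule out. If 0.50 is the intended margin, the plan enrols far more patients than its own power target needs and gives no reason.

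**Working it through.** **Inputs (Section 10.2).** Means (variances): LTAP 1.49 (1.77), UTAP 1.49 (1.77), placebo 3.40 (1.50). UTAP effect d = 3.40 − 1.49 = 1.91 cm. Allocation weights 0.4, 0.4 and 0.2. One-sided alpha 0.025, power 0.90 for each test. The documents do not define the code argument `Delta`. I read it as theta because Section 10.2 lists the non-inferiority fraction among the required inputs and no other argument in the call can carry it.

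**Formulas.** The variance factor is

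S(θ) = 1.77/0.4 + θ²·1.77/0.4 + (1−θ)²·1.50/0.2

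- S(0.70) = 4.425 + 2.168 + 0.675 = 7.268
- S(0.50) = 4.425 + 1.106 + 1.875 = 7.406

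The normal approximation is N = (1.960 + 1.2816)²·S(θ) / [(1−θ)·1.91]², with (1.960 + 1.2816)² ≈ 10.507.

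- θ = 0.70: 10.507 × 7.268 / 0.573² = 232.6
- θ = 0.50: 10.507 × 7.406 / 0.955² = 85.3

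The t version uses a noncentral t with N − 3 degrees of freedom and noncentrality (1−θ)·1.91/√(S/N). At N = 235 the noncentrality is 0.573/0.1759 = 3.258 for 0.70 and 0.955/0.1775 = 5.379 for 0.50.

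**Reproducing the plan's figure, then applying the stated fraction.**

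| | θ = 0.70 (code) | θ = 0.50 (text and rule) |
|---|---|---|
| N for 90% power, normal | 232.6 | 85.3 |
| Smallest N for 90% power, t | 235 (90.05%; 234 gives 89.93%) | 88 (90.2%); 90 in whole 2:2:1 blocks |
| Power with 235, t | 90.05% | 99.97% |
| Power with 235, simulated (400,000 trials) | 89.9% | 99.97% |

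So 235 is reproduced exactly at 0.70. Other settings at 0.50 do not reach it: alpha 0.0125 gives 101, alpha 0.005 gives 121, 95% power gives 106, a common variance of 1.7 gives 86, and reading the variances as standard deviations gives 146.

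**What the two margins mean on the VAS.** The tolerated loss at d = 1.91 is 0.50 × 1.91 = 0.955 cm, or 0.30 × 1.91 = 0.573 cm. With planned variances and an observed UTAP–placebo difference of 1.91 cm, the bound clears θ once observed retention exceeds θ + 1.970·√(S/235)/1.91.

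- θ = 0.50: 0.50 + 1.970 × 0.1775/1.91 = 0.683, an LTAP mean below 3.40 − 0.683 × 1.91 = 2.10 cm
- θ = 0.70: 0.70 + 1.970 × 0.1759/1.91 = 0.881, an LTAP mean below 3.40 − 0.881 × 1.91 = 1.72 cm

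**How often the choice decides the result.** In 400,000 simulated trials with planned variances, the share passing at 0.50 but failing at 0.70 was about 10% at true retention of 100% (the planning value), 41% at an assumed 90%, and 71% at an assumed 80%.

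**Sensitivity at 0.70.** The documents give no dropout rate, so these are illustrative. An assumed 5% loss (N = 223) gives 88.5% power and 10% (N = 211) gives 86.7%. An assumed true difference of 1.5 cm with N = 235 gives 72%; at θ = 0.50 the same case gives 98.8%.

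**The case against.** The strongest reply is that the prespecified test is not ambiguous. Sections 10.2 and 10.3 both state 0.50 in words, 0.7 appears once inside a line of code, and the analyst knows what to do. Under that rule type I error stays at 2.5% and the trial has more power than claimed, so its validity is not weakened. All of this stands. It does not rescue the statement that 235 patients are required for 90% power at 0.50. Nor is the code line a harmless misprint: if it were, 0.50 would reproduce 235, and it does not.

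Three further points are fair.

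- The 41% and 71% figures show how far apart the margins are. They are not an error rate of the trial, since only the 0.50 verdict is prespecified.
- Reading `Delta` as theta is an inference, though 0.7 returning exactly 235 leaves little doubt.
- If 0.70 were adopted, 235 leaves no room below the 90% set for each test, but the plan's overall target is 80%. With step 1 above 99%, overall power is close to that of step 2, and about 180 evaluable patients (a loss of about 23%) would still give 81%.

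**Conclusion.** The concern holds. The sample size of 235 was derived for a retention fraction of 0.70, and the statement that it gives 90% power at 0.50 is wrong. At 0.50 the power is about 99.97%, and 235 is about 2.6 times the 90 patients that 90% power needs (235/90), or 145 more. The error lies in the power statement and in the mismatch between the sizing margin and the tested margin, not in type I error. The documents cannot settle which margin was intended. These results take the plan's means and variances as printed and assume no losses. The loss rates, the 1.5 cm difference and retention below 100% are my assumptions. This must be fixed because it concerns the margin of the trial's central claim.

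**What to change.** Before any outcome data by arm are examined, the sponsor should fix one theta, justify it, and align the sample size sentence and code in Section 10.2 with the Fieller rule in Section 10.3. The hypothesis H02 is written with the symbol and needs no edit.

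- **If 0.50 is kept:** change the code to `Delta = 0.5`, state that 235 gives more than 99.9% power at the planning values and that about 88 to 90 would give 90%, and give the reason for the larger trial.
- **If 0.70 was intended:** change 0.50 and 50% to 0.70 and 70% in Sections 10.2 and 10.3. State that 235 gives 90% power only with no losses and only if the 1.91 cm difference holds. Neither is assured. The analysis set is restricted: "All analyses will be performed on patients who undergo surgery and have a 24 hour VAS pain score assessment". The control arm is also active ("Placebo groups will receive direct injection of bupivacaine into surgical wounds"), whereas the historical comparators in Section 1.1 were saline blocks or no block.

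Either route changes wording only and adds no patients. The first means acknowledging a trial larger than 90% power needs. The second sets a stricter bar, with power below 90% once any patient is lost, though still above the 80% overall target at modest loss. The choice should be dated, because "Investigators cannot be blinded due to the nature of the intervention" and a margin chosen after results by arm are known would not be credible.

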10.3 Data Analyses Plans

Analysis of Co-Primary Endpoints:

The distribution of VAS pain scores in each group will be examined and assessed for normality and homoscedasticity, visually, by generating probability-probability (P-P) plots, boxplots, stem-and-leaf plots and quantile-quantile (Q-Q) plots, and with the Shapiro-Wilk normality test. If necessary, a transformation of the data will be made to render appropriate for parametric testing. All analyses will be performed on patients who undergo surgery and have a 24 hour VAS pain score assessment. Balance on baseline characteristics (including gender, age at surgery, height, weight, BMI, and operative time) among the randomized groups will be assessed separately for each intervention, using the standardized difference. Any variable with an absolute standardized difference >0.52 (i.e., $1.96 \times 1/n_1 + 1/n_2$) for either intervention will be adjusted for in secondary analyses.^{13,14}

A step-down hierarchical hypothesis testing approach will be used to test the two hypotheses (co-primary endpoints). In the first step, to establish assay sensitivity, the alternative hypothesis that the 24-hour post-operative mean VAS pain score in the UTAP group is superior to that in the placebo group will be tested by a one-sided two sample t-test at the 0.025 level of significance ($H_{01}: \mu_{UTAP} \geq \mu_{Placebo}$ vs. $H_{A1}: \mu_{UTAP} < \mu_{Placebo}$).

If assay sensitivity is demonstrated in the first step by rejecting the null hypothesis, H_{01} , we will proceed to the second step of testing for non-inferiority of LTAP to UTAP. To establish non-inferiority, the alternative hypothesis that LTAP is non-inferior to UTAP will be tested using the ‘fractional approach’ introduced by Pigeot et al (2003) where the effect estimate is based on the ratio of the differences in means between LTAP and placebo and UTAP and placebo ($H_{02}: \frac{\mu_{LTAP} - \mu_{Placebo}}{\mu_{UTAP} - \mu_{Placebo}} \leq \theta$: vs. $H_{A2}: \frac{\mu_{LTAP} - \mu_{Placebo}}{\mu_{UTAP} - \mu_{Placebo}} > \theta$).

θ is pre-specified as the fixed fraction of active reference effect (retention of effect) of 0.50 (LTAP has to achieve more than 50% of the effect of UTAP compared to placebo to claim as non-inferior). The second step will be carried out based on the Fieller’s one-sided 97.5% lower confidence bound for the ratio of $\mu_{LTAP} - \mu_{Placebo}$ and $\mu_{UTAP} - \mu_{Placebo}$. If the lower bound of the confidence interval is greater than 50% then the null hypothesis, H_{02} is rejected (LTAP (the experimental approach) retains more than 50% efficacy of UTAP (the active reference) then non-inferiority of LTAP to UTAP will be declared. The formula for calculating Fieller’s confidence bound is presented in Pigeot et al (2003) and will be implemented using The R package ‘ThreeArmedTrials’ developed by Tobias Muetze (2016).

Analysis of Secondary Endpoints:

The secondary endpoints of 24-hour cumulative post-operative opioid analgesic requirement expressed in morphine equivalent dose (MED), intraoperative time taken to complete the surgical block, total operating room time and surgical time will be summarized using median, 1st and 3rd quartiles and minimum and

maximum values. A Kruskal-Wallis analysis of variance will be used to compare the cumulative MED requirement (time to complete the surgical block, total operating room time and surgical time) among the three intervention groups with all pairwise comparisons made between groups using the Dwass-Steel-Critchlow-Fligner procedure (Dwass 1960; Steel 1960; Critchlow and Fligner 1991).¹⁵⁻¹⁷

The secondary endpoint of antiemetic medication use will be reported as the number and percentage of patients that require antiemetic medication during their hospital stay within each intervention group. A Chi-Square will be used to compare percentages across groups. A log-binomial regression model will be used to estimate and compare the prevalence ratios (PR) and corresponding 95% confidence intervals (CI) for antiemetic medication use among patients in the three intervention groups.

The secondary endpoints, including length of hospital stay and days to return of bowel function will be analyzed depending on existence of event censoring and/or occurrence of competing events at the time of analysis. Length of hospital stay will be calculated as the number of days between the date of surgery and the date of discharge from the hospital. Days to return of bowel function will be calculated as the number of days between the date of surgery and the date of first bowel movement. If the event is observed in all patients and there is no censoring at the time of analysis, the mean and standard deviation (if normally distributed) or median and IQR (if skewed) will be presented and an analysis of variance (or Kruskal-Wallis analysis of variance) will be used to compare means (or distributions) among groups, respectively. If the event is not observed in all patients (censoring at time of analysis) then the method of Kaplan-Meier will be used to estimate the median times to event and corresponding 95% confidence intervals will be constructed based on the method of Brookmeyer and Crowley.¹⁸ Comparisons of time to event distributions among intervention groups will be made with the log-rank test. If competing events are observed, such as death prior to the event of interest, then cumulative incidence functions (CIF) will be estimated in a competing risk setting. In these analyses, discharge and first bowel movement will be the defining events in each analysis while death without discharge or prior bowel movement will be considered the competing event. Patients who are alive and have not yet been discharged or have not had return of bowel function as of the data analysis cutoff will be censored. CIF comparisons among intervention groups will be made with Gray's test.¹⁹

The secondary endpoint of procedure related complications including bleeding or injection of anesthetic intravascular will be determined according to Common Terminology Criteria for Adverse Events (CTCAE v 4.0) and presented as frequency at each grade. A Poisson regression model will be used to test the difference in adverse event rates between the two groups. In this model, the numerator is the number of adverse events and the denominator (offset) is the natural log of the person days followed.

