6.0 Measurement of Effect**6.1 Pain Scale****6.1.1 Definition**

Patient solicited pain scores will be assessed using the Visual Analogue Pain Scale (VAS-Pain). VAS is a pain rating scale where scores are based on self-reported measures of symptoms that are recorded with a single handwritten mark placed at one point along the length of a 10-cm line that represents a continuum between the two ends of the scale—“no pain” on the left end (0 cm) of the scale and the “worst pain” on the right end of the scale (10 cm). Measurements from the starting point (left end) of the scale to the patients' marks are recorded in centimeters and are interpreted as their pain intensity. This will be administered by asking the patient to place a line perpendicular to the VAS line at the point that represents the pain intensity. This pain scale is commonly used throughout the pain literature and takes <1 minute to complete.

Further explanation may be found here:

<https://onlinelibrary.wiley.com/doi/full/10.1002/acr.20543>

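### An unspecified, data-driven transformation of VAS ahead of the retention test would change the non-inferiority margin while theta stays at 0.50

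*Combined protocol and SAP*

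**What the plan says.** Section 10.3, under the analysis of the co-primary endpoints, opens with a distributional check: "The distribution of VAS pain scores in each group will be examined and assessed for normality and homoscedasticity". The check uses several plots and the Shapiro-Wilk test. The consequence follows: "If necessary, a transformation of the data will be made to render appropriate for parametric testing". Both primary tests are described after this, and neither is exempted.

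The second test (H02) uses the fractional approach, "where the effect estimate is based on the ratio of the differences in means between LTAP and placebo and UTAP and placebo". It is judged by a one-sided 97.5% Fieller lower bound against theta = 0.50, explained as "LTAP has to achieve more than 50% of the effect of UTAP compared to placebo to claim as non-inferior".

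The scale is set elsewhere. Section 6.1.1 has marks on a 10-cm line that "are recorded in centimeters and are interpreted as their pain intensity". The planning values in Section 10.2 are on that scale: "assuming means and variances of 1.49 (1.77), 1.49 (1.77) and 3.40 (1.50) in the LTAP, UTAP and Placebo groups".

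The plan names no transformation, sets no threshold for using one, does not say how scores of 0 cm would be handled (a plain log is undefined there), and does not restate theta on a new scale.

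**The concern.** A retention fraction has meaning only on a stated scale. Half the distance between two means in centimetres is not half the distance between the means of square roots or logs. If the scores are transformed and 0.50 is kept, the primary decision is made against a different margin from the declared one. That margin is also settled after the outcome has been inspected group by group, in a trial whose investigators know the allocation (Section 10.1). The choice of scale then becomes a choice of margin. What is at stake is the trial's main claim, that LTAP retains more than half of UTAP's effect over local bupivacaine.

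**Working it through.** **Inputs.** From Section 10.2: means (variances) of LTAP 1.49 (1.77), UTAP 1.49 (1.77) and placebo 3.40 (1.50); 94/94/47 patients; one-sided alpha 0.025; 90% power per test. From Section 10.3: theta = 0.50. Assumed, because the documents give none: gamma or scaled-beta score shapes, the square-root and log(1+x) transformations, and LTAP variances other than 1.77.

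**1. The plan's own figure.** With E, R and P for LTAP, UTAP and placebo,

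N = (1.960 + 1.282)² × [vE/0.4 + θ²·vR/0.4 + (1−θ)²·vP/0.2] / [(1−θ)(μP − μR)]²

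- θ = 0.7: 10.507 × (4.425 + 2.168 + 0.675) / 0.573² = 10.507 × 7.268 / 0.3283 = 232.6, close to the stated 235.
- θ = 0.5: 10.507 × (4.425 + 1.106 + 1.875) / 0.955² = 10.507 × 7.406 / 0.9120 = 85.3.

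So 235 follows from the printed code ("Delta = 0.7, sig_level = 0.025, power= 0.9"), not from the 0.50 in the text. That conflict is a separate point. Here it shows that the sizing is entirely on raw means. Everything below uses 0.50.

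**2. The declared boundary in cm.** UTAP effect = 3.40 − 1.49 = 1.91 cm. Half retained puts the LTAP mean at 3.40 − 0.5 × 1.91 = 2.445 cm, which is 0.955 cm above UTAP.

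**3. The same 0.50 after transformation, means only.**

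- Square root: midpoint of √1.49 = 1.2207 and √3.40 = 1.8439 is 1.5323; squared, 2.348 cm. Raw retention (3.40 − 2.348)/1.91 = 55.1%; allowed excess over UTAP 0.858 cm.
- log(1+x): midpoint of ln 2.49 = 0.9123 and ln 4.40 = 1.4816 is 1.1969; back-transformed, 2.310 cm. Raw retention 57.1%; allowed excess 0.820 cm.

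**4. Full distributions.** Three arms were simulated under gamma and scaled-beta shapes, and the θ = 0.50 test was applied to raw, square-root and log(1+x) scores.

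| LTAP variance | True raw retention | Retention on transformed scale | NI declared, raw | NI declared, transformed |
|---|---|---|---|---|
| 1.77 (plan) | 50% | about 0.43 | 2.5-2.8% | 0.2-0.3% |
| 1.77 (plan) | 70% | 0.63-0.64 | 57-58% | 33-38% |
| 1.77 (plan), LTAP = UTAP | 100% | 1.00 | above 99% | above 99% |
| 3 (assumed) | 50% | 0.49-0.51 | about 3% | about 2-3% |
| 4 (assumed) | 50% | 0.53-0.57 | 3-4% | about 5-10% |

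The shift is conservative at the planning variances, nearly vanishes at the boundary when the LTAP variance is about 3, and reverses above that.

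**5. How likely is a transformation?** A normal curve with mean 1.49 and SD √1.77 = 1.33 puts Φ(−1.12), about 13%, below zero, so the planning values imply skewness. At n = 94 Shapiro-Wilk rejects in essentially all gamma or beta samples with these values. With the robotic prostatectomy trial's UTAP values (1.80, SD 0.82) it rejects in about 75-90% under gamma or beta, but in under 5% under a normal clipped at zero.

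**The case against.** **The transformation may never happen.** The wording leaves it to judgement, and a low Shapiro-Wilk p-value is only one of several things to be looked at. The planning variance of 1.77 is a meta-analytic total that exceeds the UTAP variance in three of the four source trials (1.44, 0.35 and 0.67). Under a normal clipped at zero with the planning values, Shapiro-Wilk still rejects in over 99% of samples after a square root or log(1+x), so neither would cure the problem. A reader might infer from the skewness that a transformation is close to certain. The documents do not support that, because they set no trigger. This part of the objection stands.

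**The shift is harmless because it is conservative.** At the planning variances it does make a false claim rarer, and under the design alternative (LTAP equal to UTAP) nothing is lost. The 70% retention case is not a design alternative. But the protection depends on the LTAP variance, which nobody knows. The values of 3 and 4 are assumptions. They are not outlandish: Section 10.2 lists variances of 4.00 and 5.29 in two historical placebo arms. A reader might equally infer that transformation generally inflates the error, or that the planned power collapses. Neither follows.

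**The margin is a fraction, never a number of centimetres.** True, but the hypotheses are written in mean VAS, VAS is defined in centimetres, and the planning means are on that scale. The raw scale is the natural reading, and the plan restates theta on no other.

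**Conclusion.** The point holds for H02. As written, the plan permits an unnamed transformation, chosen after seeing the outcome, to redefine the margin of the primary non-inferiority test. That only linear transformations preserve the ratio is a mathematical fact and needs no assumption. The size does: it depends on the assumed score shapes, the transformation and, above all, the LTAP variance, and it can go in either direction.

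The consequence falls where LTAP is somewhat worse than UTAP, which is the case that a non-inferiority test exists to judge. Step 1 is a superiority comparison without a margin and is little affected; a reader should not infer that the assay-sensitivity test is compromised.

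Nor is a transformation needed for validity here. At the planning variances the raw-scale test rejected in about 2.5-2.8% at the boundary despite strong skew. It drifts to 3-4% at LTAP variance 4, which is a reason for a sensitivity analysis on the raw scale, not for changing the scale.

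**What to change.** Before any outcome data are examined by group, replace the transformation sentence in Section 10.3 with wording to this effect:

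- The Fieller bound for H02 and, for consistency, the step 1 t-test are computed on untransformed 24-hour VAS in cm whatever the normality checks show, with variances not assumed equal. Section 10.2 already sizes step 1 with an unequal-variance t-test; Section 10.3 does not say which form is used.
- A studentised bootstrap of the H02 contrast (LTAP mean − θ × UTAP mean − (1 − θ) × placebo mean) on raw cm is the sensitivity analysis for skewness. A permutation test is not suitable for H02, because the arms are not exchangeable at its boundary.
- Any analysis of transformed scores is supportive only.

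Naming one transformation in advance and restating theta on it would also be coherent, but the retained fraction would be harder to explain.

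The cost is a short SAP amendment and a short bootstrap script, with no added patients or data. The conflict between theta = 0.50 in the text and Delta = 0.7 in the sample-size code must be reconciled separately; the figures above would need to be rerun if theta changes.
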